7.6.3 PRO-CTCAE

The PRO-CTCAE is a patient-reported outcome measure developed to evaluate symptomatic toxicity in patients participating in oncology clinical trials. It was designed to be used as a companion to the Common Terminology Criteria for Adverse Events (CTCAE), the standard lexicon for adverse event reporting in cancer trials. PRO-CTCAE includes an item library of 124 items representing 78 symptomatic toxicities drawn from the CTCAE. PRO-CTCAE provides a systematic yet flexible tool for descriptive reporting of symptomatic treatment side effects in cancer clinical trials. Selected items from the PRO-CTCAE will be administered. The PRO-CTCAE uses a recall period of “the last 7 days.”

To report the PRO-CTCAE data, the tabulation of the maximum score post-baseline per patient per item will be used, and it will be presented by treatment group. A by-patient listing of PRO-CTCAE will also be provided.

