Brain Imaging	
 Patients with a history of brain metastasis or neurological symptoms should have MRI with and without contrast. See Section 7.2 if patient has contraindications to contrast MRI. Performed on same schedule as body tumor assessments, and as clinically indicated Tumor assessments will continue until both BICR and Investigator’s assessments of tumor images have determined progression. Patients who are receiving study treatment beyond progression should continue scans until the criteria for treatment discontinuation are met and BICR-assessed progression has occurred. Tumor assessments are no longer required if subsequent anticancer therapy is started, even if the patient has not yet progressed. Use same imaging method as was used at screening. 						All study treatment decisions will be based on the Investigator’s assessment of tumor images. See Section 7.0 for further details.	
Pharmacokinetic and Biomarker Assessments								
	■				■	■		
NKTR-214 PK Blood Samples	X	X	X	X	X	Z	Z = Cycles 3, 6, 9, 12, and 15 only See Table 6 and Section 5.9 for further details.	
Nivolumab PK Blood Samples	X				X	Z	Z = Cycles 3, 6, 9, 12, and 15 only See Table 6 and Section 5.9 for further details.	
Tumor Tissue Sample							Optional Cycle 1 Day 14-21 and at disease progression. See Section 5.10.1 for further details.	

Abbreviations used in this table appear on the final page of Table 4.

Table 2: On-Treatment Schedule of Events for Arm A (Contd)

Procedure ^a	Arm A NKTR-214 0.006 mg/kg IV q3w and Nivolumab 360 mg IV q3w Cycle = 6 Weeks							Notes
	Cycle 1					Cycle 2 and all subsequent cycles		
	Day 1	Day 3 (-1 day)	Day 5 (± 1 day)	Day 8 (-1 day)	Day 22 (± 3 days)	Day 1 (± 3 days)	Day 22 (± 3 days)	
██████████ ██████████ ██████████ ██████████	■				■	■		████████████████████ ████████████████████ ████████████████████ ████████████████████ ████████████████████ ████████████████████ ████████████████████ ████████████████████ ████████████████████ ████████████████████
Outcomes Research Assessments								
EQ-5D-3L	X				X	X	X	Patients should complete the assessment at the start of the clinic visit, prior to dosing and scheduled activities.
FKSI-19	X				X	X	X	
PRO-CTCAE	X				X	X	X	Completed on Days 1 and 22 of every cycle through Cycle 4, and then on Day 1 of all subsequent cycles. See Section 7.6 for further details.
Health Care Resource Utilization	X				X	X	X	Site staff will collect health care resource utilization data using the CRF.

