EQ-5D-3L	X		X	X	X	Patients should complete the assessment at the start of the clinic visit, prior to dosing and scheduled activities.
FKSI-19	X		X	X	X	
PRO-CTCAE	X		X	X	X	Completed on Days 1 and 22 of every cycle through Cycle 4, and then on Day 1 of the following cycles. See Section 7.6 for further details.

Abbreviations used in this table appear on the final page of [Table 4](#).

Table 3: On-Treatment Schedule of Events for Arm B (Contd)

Procedure ^a	Arm B Cabozantinib 60 mg PO once daily (continuously) OR Sunitinib 50 mg PO once daily (4 weeks on treatment, followed by 2 weeks off treatment) Cycle = 6 Weeks					Notes
	Cycle 1			Cycle 2 and subsequent on-treatment visits		
	Day 1	Day 8 (-1 day)	Day 22 (± 3 days)	Day 1 (± 3 days)	Day 22 (± 3 days)	
Health Care Resource Utilization	X		X	X	X	Site staff will collect the health care resource utilization data at each visit using the CRF.

a. Assessments and visits that occur outside of protocol-specified windows (e.g., for holidays, travel issues, insurance issues) may be acceptable on a case-by-case basis after review by the Medical Monitor.

Abbreviations used in this table appear on the final page of [Table 4](#).

Table 4: Long-Term Follow-Up Schedule of Events

Procedure ^a	Safety Follow-Up Visit 1 ^b	Safety Follow-Up Visit 2 ^b	Survival Follow-Up ^c Every 12 Weeks (± 14 days)	Notes ^d
Safety Assessments				
Vital Signs	X	X		Blood pressure, heart rate, temperature Weight
AE and SAE Assessments	X	X	X	All AEs will be documented until 100 days after the last dose of all study drug(s). SAEs to be collected after the 100-day safety visit if the SAE is deemed to be related or residual toxicities are persisting. Patients will be followed for drug-related toxicities until these toxicities resolve, return to baseline, or are deemed irreversible.
Karnofsky Performance Status	X	X		See Appendix 2 .
Review of Subsequent Medications and Anticancer Therapy	X	X	X	In Survival Follow-up, subsequent anticancer treatment only. Additional subsequent anticancer therapy details such as regimen, setting of the regimen, line of therapy, start date and end date of each regimen, best response to the regimen, and date of progression to subsequent anticancer therapies will be collected.
Laboratory Tests				
Pregnancy Test (WOCBP only)	X	X		Patients (WOCBP) will continue to follow instructions for methods of contraception through 5 months post treatment completion.

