PRO-CTCAE	
Summary statistics for PRO-CTCAE at each assessment point and per item will be summarized for each treatment group. The mean change from baseline will also be reported at each post baseline assessment point.

HCRU	
Summary statistics for HCRU at each assessment point will be summarized for each treatment group.

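### PRO-CTCAE is summarized only as an unadjusted worst post-baseline score, which mixes pre-existing symptoms into each arm's rate, and no workable baseline is defined for it

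*SAP*

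**What the plan says.** - **SAP 7.6.3** plans one summary, by treatment group: "the tabulation of the maximum score post-baseline per patient per item will be used". The only other output is a listing: "A by-patient listing of PRO-CTCAE will also be provided". The same section describes the instrument as a tool for "descriptive reporting of symptomatic treatment side effects in cancer clinical trials".
- **Protocol 9.5**, in the PRO-CTCAE row, plans summary statistics per item at each assessment point by treatment group, and adds: "The mean change from baseline will also be reported at each post baseline assessment point".
- **Protocol 1.2** marks PRO-CTCAE at Cycle 1 Day 1 in both arms. The Arm A note reads "Completed on Days 1 and 22 of every cycle through Cycle 4, and then on Day 1 of all subsequent cycles" and the Arm B note "Completed on Days 1 and 22 of every cycle through Cycle 4, and then on Day 1 of the following cycles". Both on-treatment tables also carry the outcomes-research instruction "Patients should complete the assessment at the start of the clinic visit, prior to dosing and scheduled activities". SAP 7.6 likewise puts completion before the first dose.
- **Protocol Table 1 (Screening)** lists FKSI-19 and EQ-5D-3L but not PRO-CTCAE.
- **SAP 6.6** sets baseline in general as the last result on or before randomization. The exception that runs to first dose is for safety assessment data and names laboratory and vital-sign data only. It also notes that the first dose may follow randomization by up to 5 days.

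**The concern.** A post-baseline maximum shows how bad a symptom was while the patient was on study. It does not show whether the symptom was there before any drug was given. In advanced renal cell carcinoma some patients can be expected to arrive with symptoms. At least 500 of about 600 are to be intermediate or poor risk, and a Karnofsky status of 70 is allowed. A reader who takes the table as a report of treatment side effects, which is how the SAP introduces the instrument, will read too high a rate in each arm and too small a relative contrast between them.

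Pre-dose data exist that would separate the two, and the protocol planned to use them. The SAP drops that analysis without comment; its document history (Section 13.0) does not mention PRO-CTCAE.

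**Working it through.** The documents give no rate, threshold, sample size or power for PRO-CTCAE, so there is no stated figure to reproduce. The check is a comparison of texts plus an illustration on declared assumptions.

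**1. How baseline is used elsewhere**

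| Measure | Use of baseline |
|---|---|
| FKSI-19 (SAP 7.6.1) | Change from baseline; baseline score is a model covariate |
| EQ-5D index and VAS (SAP 7.6.2) | Mean change from baseline |
| Laboratory grades (SAP 8.5.1 to 8.5.3) | Counts of patients whose grade rose from baseline |
| Adverse events (Protocol 8.1) | Pre-existing conditions that do not worsen are not AEs |
| PRO-CTCAE (Protocol 9.5) | Per-visit summaries and mean change |
| PRO-CTCAE (SAP 7.6.3) | None |

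**2. Size of the effect**

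Let b be the share of patients at or above a chosen score before the first dose, equal in the arms by randomization. Let e be the share of the others who newly reach it on treatment. Let r be the share of pre-existing symptoms that would be reported again at least once after baseline without any new effect of treatment. Further worsening in patients already at the threshold is ignored. None of b, e and r is in the documents.

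- Unadjusted rate: b[r + (1 − r)e] + (1 − b)e. With r = 1 this is b + (1 − b)e.
- Baseline-adjusted rate (counted only if worse than baseline): (1 − b)e.
- Inflation per arm: b[r + (1 − r)e], which is at most b.

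With e = 30% in one arm and 20% in the other, the true ratio is 1.5. For r = 1:

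| b | Unadjusted | Adjusted | Difference, unadjusted / adjusted (points) | Unadjusted ratio |
|---|---|---|---|---|
| 10% | 37% vs 28% | 27% vs 18% | 9 / 9 | 1.32 |
| 20% | 44% vs 36% | 24% vs 16% | 8 / 8 | 1.22 |
| 30% | 51% vs 44% | 21% vs 14% | 7 / 7 | 1.16 |
| 40% | 58% vs 52% | 18% vs 12% | 6 / 6 | 1.12 |

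For r = 0.5 the unadjusted rates are 33.5% vs 24% at b = 10% and 44% vs 36% at b = 40%. Inflation is then 6 to 6.5 points and 24 to 26 points, and the ratios are 1.40 and 1.22. The unadjusted differences are 9.5 and 8 points, against 9 and 6 adjusted.

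**3. Chance imbalance**

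With 300 patients per arm (protocol synopsis) and b = 20%, the standard error of the baseline difference is √(2 × 0.2 × 0.8 / 300) = 3.3 points. With r = 1, the unadjusted rate changes by (1 − e) per unit of b, so at e of 20% to 30% one standard error moves the arm difference by about 2.3 to 2.6 points. Its expected value is zero.

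**4. Which score is baseline**

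PRO-CTCAE is not scheduled at Screening, so the first score is at Cycle 1 Day 1. If that day falls 1 to 5 days after randomization, the general rule in SAP 6.6 does not accept the score as baseline. The exception does not clearly reach it, because it names laboratory and vital-sign data and PRO-CTCAE sits in the quality-of-life section. Read literally, such a patient has no baseline, and a score given before any drug may enter the post-baseline maximum. Some SAP 7.6 wording could suggest completion before randomization for all instruments, but the protocol's Screening table does not schedule PRO-CTCAE.

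**The case against.** The strongest reply is that this is a descriptive table. It has no test, no attribution to drug and no place in the alpha structure. Toxicity conclusions will rest on the treatment-emergent and drug-related AE tables, where the protocol's AE definition already excludes unchanged pre-existing conditions. Randomization balances pre-existing symptoms in expectation, and the listing should show the Cycle 1 Day 1 scores. All of this stands and limits the weight of the point. It does not close the gap: a listing is not a summary, and the SAP still omits what the protocol planned.

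It is also fair to say that an adjusted maximum alone can mislead, since a patient with a persistently high score then looks unaffected. That is a reason to show it beside the unadjusted table, not in its place.

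A reader might infer three stronger things that the documents do not support:

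- **That the arm comparison is biased.** Under the model with full recurrence the difference in points is the same with and without adjustment. What changes is the level in each arm and the ratio.
- **That one arm's maximum is raised because it has more assessments.** The planned schedule is the same in both arms and no actual counts are given. Time on treatment could make counts diverge, for example through the two-year cap in Arm A only, but a baseline-adjusted maximum would grow with the number of assessments too.
- **That unchanged baseline symptoms will be reported as severe toxicity.** The documents give neither the response scale nor the list of selected items, so no score can be labelled that way from them.

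**Conclusion.** The point holds as a should-fix on reporting and consistency. SAP 7.6.3 omits every baseline-related PRO-CTCAE summary, although pre-dose scores are collected in both arms and Protocol 9.5 plans to use them. Each arm's rate is inflated by up to roughly the baseline prevalence of the symptom, and the ratio of the arms is pulled toward 1. The 10 to 40 point range rests on assumed prevalence, assumed onset rates and full recurrence; with half recurring, inflation is about 6 to 26 points. The randomized difference is not systematically biased, but chance imbalance passes through. The baseline definition in SAP 6.6 is a separate gap and must be settled first, because any adjustment depends on it.

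**What to change.** 1. In SAP 6.6 and 7.6.3, define PRO-CTCAE baseline as the last score before the first dose, so that a pre-dose Cycle 1 Day 1 score is never counted as post-baseline.
2. Add a tabulation of baseline scores by item and arm.
3. Keep the unadjusted maximum and show beside it a baseline-adjusted maximum by item and arm, in which the post-baseline maximum counts only if it is worse than baseline.
4. Restore the per-visit and change-from-baseline summaries of Protocol 9.5, or withdraw them explicitly with a reason.

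The cost is one definition, one derivation and a few descriptive tables. No new data are needed, and no alpha or sample-size element is affected.

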5.4 Treatment Period

Patients will be treated until a maximum of 2 years from Cycle 1 Day 1 (Arm A only), disease progression per mRECIST 1.1 in the absence of clinical benefit as determined by the Investigator, death, unacceptable toxicity, symptomatic deterioration, the Investigator's decision to discontinue treatment, the patient decides to discontinue treatment or withdraw consent, the patient is lost to follow-up, or termination of the study by the Sponsor.

Patients with PD per mRECIST 1.1 but with otherwise stable or improved performance and clinical status may continue to be treated in the event of a perceived benefit per Investigator; see [Section 5.4.4](#) for treatment beyond progression. Patients with a partial response (PR) or with stable disease (SD) will continue to receive study drugs until disease progression, or intolerability to therapy. It is at the discretion of the Investigator to continue treating patients with a confirmed CR, for a maximum treatment of 2 years from Cycle 1 Day 1 (Arm A only).

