5.4.3 Duration of Treatment

Patients will remain on treatment until:

- Disease progression in the absence of clinical benefit as determined by the Investigator
- Death
- Unacceptable toxicity

- Symptomatic deterioration
- 2 years from Cycle 1 Day 1 (Arm A only)
- Investigator's decision to discontinue treatment
- Patient decision to discontinue treatment
- Patient withdraws consent
- Patient is lost to follow-up
- The Sponsor decides to terminate the study

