5.6.1 Safety Follow Up

- Safety Follow-up Visit 1 should occur 30 (± 7) days from the last dose of all study drug, or at the time of permanent treatment discontinuation if discontinuation is after the Safety Follow Up Visit 1 window.
- Safety Follow-up Visit 2 occurs 100 (± 7) days from the last dose of all study drug. Safety follow-up visits should occur regardless of initiation of subsequent anticancer therapy.
- Both Safety Follow-Up Visits should be conducted in person.
- Per clinical judgment, the patient may come in earlier for additional follow up.

- Patients will also be followed for safety until resolution or permanent sequelae of all toxicities attributable to study drugs (NKTR-214 and/or nivolumab or TKI) as outlined in Sections 8.5 and 8.8.
- For AE and SAE reporting periods, please refer to Sections 8.5 and 8.7.

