5.13 Dosage Modification

Every effort should be made to follow planned dosing schedules for all study drugs in both treatment arms. Study drug administration may be delayed or modified for toxicity as described below and must be discontinued as required by criteria described in Section 5.14.

Dose modification for NKTR-214 and nivolumab in Arm A may be considered independently based on Investigator assessment of relationship of a toxicity to each of the study drugs. If only one of the study drugs meets the criteria for dose delay, then administration of the other study drug may be continued or delayed at the discretion of the Investigator. Likewise, in the event that one of the study drugs in Arm A is permanently discontinued due to toxicities, the other can continue to be administered.

Patients who require delay of nivolumab or NKTR-214 should be re-evaluated weekly or more frequently if clinically indicated and should resume treatment with combination of NKTR-214 and nivolumab when retreatment criteria are met (Section 5.13.7). Immuno-oncology agents are associated with AEs that can differ in severity and duration from AEs caused by other therapeutic classes. NKTR-214 and nivolumab are considered an immuno-oncology agent in this protocol. Early recognition and management of AEs associated with immuno-oncology agents may mitigate severe toxicity.

For patients randomized to Arm A: NKTR-214 or nivolumab administration defines a scheduled nominal dosing visit (i.e., Cycle X Day 1, Cycle X Day 22). If a patient is assessed for an intended nominal dosing visit but study drug is not administered (e.g., due to an AE requiring dose delay, drug unavailable), any assessments performed during that visit should be recorded as “unscheduled.” When study drug administration resumes, all assessments should be performed as scheduled for the next nominal dosing visit (i.e., Cycle X Day 1 or Cycle X Day 22 Visit).

For patients randomized to Arm B: Cycle 1 Day 1 is defined by the date that the first dose of sunitinib or cabozantinib is administered. Within a cycle, missed doses of sunitinib should be skipped and not replaced. Scheduled Cycle X Day 1 and Cycle X Day 22 visits are fixed relative to Cycle 1 Day 1, regardless of dose delays. If drug dosing is delayed at the time of these scheduled visits (e.g., due to an AE requiring dose delay, drug unavailable), the cycle visit is not shifted and all assessments should be performed as scheduled.

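### SAP 7.6.3 reports PRO-CTCAE only as a whole-period maximum that grows with the number of forms, and drops the per-assessment summaries planned in Protocol 9.5

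*SAP*

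**What the plan says.** SAP 7.6.3 plans one PRO-CTCAE table: "the tabulation of the maximum score post-baseline per patient per item will be used". It is shown by treatment group and accompanied by a listing. No time window, form count, completion rate or exposure adjustment is given.

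Protocol 9.5 plans something else: "Summary statistics for PRO-CTCAE at each assessment point and per item will be summarized for each treatment group", plus mean change from baseline at each post-baseline assessment. SAP 7.6.3 contains neither.

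The form schedule is the same in both arms. Protocol 1.2, Table 2 (Arm A): "Completed on Days 1 and 22 of every cycle through Cycle 4, and then on Day 1 of all subsequent cycles". Table 3 (Arm B) matches. After treatment, Table 4 marks PRO-CTCAE only at Safety Follow-Up Visit 1, not at Visit 2 or in survival follow-up. Protocol 5.6.1 times that visit: "Safety Follow-up Visit 1 should occur 30 (± 7) days from the last dose of all study drug".

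Two features differ by arm:

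- Protocol 5.4.3 limits treatment to 2 years in Arm A only.
- Under Protocol 5.13, for Arm B, "Scheduled Cycle X Day 1 and Cycle X Day 22 visits are fixed relative to Cycle 1 Day 1, regardless of dose delays". In Arm A a nominal visit is defined by dosing, so a delay moves the next scheduled visit, and anything done at the missed visit is recorded as unscheduled.

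**The concern.** A running maximum cannot fall as forms are added. Here the number of forms follows from how long a patient stays on treatment. Two arms with identical symptom burden at every form would therefore show different proportions with a high maximum if they were treated for different lengths of time or completed forms at different rates. An arm that loses patients early, including to toxicity, would tend to look better in this table.

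At stake is how a patient-reported symptom comparison in an open-label trial is read. The SAP treats neighbouring outcomes differently. FKSI-19 and EQ-5D-3L have completion rates and summaries at each time point (SAP 7.6.1 and 7.6.2), and hospitalizations are also reported per person-year (SAP 7.7). PRO-CTCAE has none of these, so a reader of its table could not separate symptom burden from number of forms.

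**Working it through.** The plan states no PRO-CTCAE figure, so there is nothing to reproduce. The check asks how far the planned table can move when the arms do not truly differ.

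**1. Forms by time on treatment.** Assume the Cycle 1 Day 1 pre-dose form is baseline, there are no delays, and every form is completed. With 6-week cycles, post-baseline forms fall at Weeks 3, 6, 9, 12, 15, 18 and 21, then at Week 24 and every 6 weeks, plus one at Safety Follow-Up Visit 1.

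- 12 weeks: 4 + 1 = 5
- 24 weeks: 8 + 1 = 9
- 52 weeks: 12 + 1 = 13
- 104 weeks: 21 + 1 = 22

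**2. Chance of a severe maximum.** Let p be the chance of a score of 3 or more on an item at any one form (assumed 2% or 5%, equal in both arms and constant over time), and n the number of forms.

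- Independent forms: 1 − (1 − p)^n.
- Within-patient correlation ρ: beta-binomial, 1 − B(a, b + n)/B(a, b), with a = p(1 − ρ)/ρ and b = (1 − p)(1 − ρ)/ρ. For p = 5% and ρ = 0.3, a = 0.117 and b = 2.217.

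| p | ρ | 9 forms | 22 forms |
|---|---|---|---|
| 2% | 0 | 16.6% | 35.9% |
| 5% | 0 | 1 − 0.95^9 = 37.0% | 1 − 0.95^22 = 67.6% |
| 2% | 0.3 | 8.0% | 11.3% |
| 5% | 0.3 | 18.9% | 26.0% |

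**3. Difference between arms with no true difference.** Time on treatment is taken as exponential, cut at 2 years in Arm A only, and step 2 is averaged over it. As an assumed proxy for median treatment time I used PFS medians in the protocol: 11.0 and 10.4 months (PD-L1 below 1%) and 22.8 and 5.9 months (PD-L1 1% or more) from the nivolumab-ipilimumab versus sunitinib trial (Protocol 2.3.1), and 8.2 and 5.6 months from the cabozantinib versus sunitinib trial (Protocol 2.4.2). Rows pairing 11.0 with 8.2 or 5.6 cross trials; the last two rows are what-if cases.

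| Median months, A vs B | Mean forms, A vs B | A minus B, points (p 2–5%, ρ 0–0.3) |
|---|---|---|
| 22.8 vs 5.9 | 16.6 vs 9.6 | +2.4 to +19.1 |
| 11.0 vs 5.6 | 12.9 vs 9.3 | +1.4 to +10.5 |
| 11.0 vs 8.2 | 12.9 vs 12.3 | +0.4 to +3.3 |
| 11.0 vs 10.4 | 12.9 vs 14.7 | −0.2 to −1.8 |
| 11.0 vs 11.0 | 12.9 vs 15.3 | −0.3 to −2.6 |
| 5.6 vs 11.0 | 9.0 vs 15.3 | −1.7 to −13.5 |

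The +19.1 comes from p = 5% and independent forms: 54.5% − 35.4%.

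**4. Effect of thinning after Cycle 4.** At 24 months, p = 2%, independent forms: 22 forms give 35.9%; keeping both days throughout would give 35 forms and 50.7%. The thinning slows the rise.

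**5. Would a window cure it?** Limiting the maximum to forms through Cycle 4 Day 22 plus the 30-day visit (independent forms) shrinks the gap for 11.0 vs 5.6 months from 5.8 to 1.6 points (p = 2%) or 10.5 to 3.4 (p = 5%). For 22.8 vs 5.9 months it falls from 10.9 to 2.4 or 19.1 to 5.1. It does not reach zero, because early stoppers still give fewer forms.

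**Limits.** Missing forms and the different visit clocks are not modelled. Arm B has no end date in the calculation, whereas Protocol 5.7 bounds the study, so the effect of the Arm A limit alone (equal-medians row) is if anything too large. Constant risk is a simplification.

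**The case against.** The case for leaving the table alone has substance.

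- The worst score over the treatment course is a legitimate descriptive quantity, and it mirrors SAP 8.1, where each patient counts once at worst grade over the treatment-emergent period without person-time adjustment. This stands as a reason to keep the maximum. It is weaker as a reason to have nothing else: adverse events are collected continuously, while PRO-CTCAE is seen only when a form is completed.
- Exposure by arm (SAP 7.4.4) and Kaplan-Meier time to treatment discontinuation (SAP 7.5.3) are planned, so unequal exposure would be visible. That is true, but neither shows how many forms fed the maximum.
- Per-assessment summaries have their own weakness: they describe only patients still completing forms. This stands and should be stated beside them.

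A reader might also infer more than the documents support:

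- *That thinning the forms after Cycle 4 biases the comparison.* The schedule is common to both arms and, under constant risk, thinning slows the rise. The cause is an unwindowed maximum over a collection period tied to treatment.
- *That the arms are simply not comparable, or that a particular arm is favoured.* Neither document gives expected time on treatment, and the sign in the working changes with the durations assumed.
- *That the rise from 37.0% to 67.6% is the expected distortion.* It contrasts patients with 9 and 22 forms, not arms, and treats one patient's repeated reports as independent. With correlation 0.3 it is 18.9% to 26.0%.
- *That this is the trial's only patient-reported tolerability comparison.* FKSI-19 has a treatment side effects subscale, analysed at each assessment and by a repeated-measures model between arms (SAP 7.6.1).

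**Conclusion.** The point holds in a limited form. SAP 7.6.3 omits the per-assessment, per-item summaries and change from baseline that Protocol 9.5 plans, and keeps only a maximum whose value depends on the number of forms. The between-arm reading of that table is confounded to the extent that time on treatment or form completion differs between arms.

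The size cannot be fixed from the documents. With similar treatment times the artificial difference is small (under 1 to about 3 points). It approaches 19 points only under the most divergent durations tried, 5% risk per form and independent forms. These figures rest on assumed per-form risks, equal in both arms, and on PFS as a stand-in for treatment time.

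PRO-CTCAE has no planned test and no alpha, so no primary or key secondary conclusion depends on it. This is a matter of aligning the SAP with the protocol and making a descriptive table readable.

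**What to change.** In SAP 7.6.3:

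1. Restore the Protocol 9.5 analysis: score distributions per item at each assessment and change from baseline, by arm, with completion rates as already planned for FKSI-19 and EQ-5D-3L. Note that these are conditional on patients still completing forms.
2. Show the number of forms contributing per patient, by arm, beside the maximum-score table.
3. Label the whole-period maximum as exposure-dependent.
4. Optionally add a maximum over a common calendar window, for example the first 24 weeks from Cycle 1 Day 1. Calendar time is preferable to a nominal visit because Arm A visits move with dose delays. This reduces the problem but does not remove it, and symptoms that first appear later would show only in the other tables.
5. Define the PRO-CTCAE baseline and say whether forms from unscheduled visits count. Protocol Table 1 has no screening PRO-CTCAE, and the general baseline in SAP 6.6 is on or before randomization. A pre-dose Cycle 1 Day 1 form, up to 5 days later, could therefore be counted as post-baseline.

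The cost is SAP wording and a few more table shells. No new data are needed.
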